# **3** Glossary of Abbreviations

β2-M Beta2-microblogulin

β-hCG Beta - Human chorionic gonadotropin

AE Adverse event

ALT (SGPT) Alanine transaminase (serum glutamate pyruvic transaminase)

AST (SGOT) Aspartate transaminase (serum glutamic oxaloacetic transaminase)

Bid Twice per day

BM Bone marrow

BMSC Bone marrow stromal cells

BUN Blood urea nitrogen

CBC Complete blood count

CFR Code of Federal Regulations

CR Complete response

CRF Case report form

CTC Common toxicity criteria

DLT Dose-limiting toxicity

DSMP Data Safety Monitoring Plan

DVT Deep vein thrombosis

EC Ethics Committee

Page 12 of 86 Confidential

ECG Electrocardiogram

ECHO Echocardiogram

EGR1 Early Growth Response 1

EGR2 Early Growth Response 2

EGR3 Early Growth Response 3

FDA Food and Drug Administration

GCP Good clinical practice

G-CSF Granulocyte colony stimulating factor

GM-CSF Granulocyte macrophage colony stimulating factor

IB Investigator's Brochure

ICH International Conference on Harmonization

IFN-α Interferon-alpha

IL Interleukin

IMiD Immunomodulatory drug

IMWG International Myeloma Working Group

IND Investigational New Drug

IRB Institutional Review Board

IVP Intravenous push

LDH Lactate dehydrogenase

mAbs Monoclonal antibodies

Page 13 of 86 Confidential

MM Multiple myeloma

MTD Maximum tolerated dose

NCI National Cancer Institute

NK cells Natural Killer Cells

PBMC Peripheral blood mononuclear cells

PD Progressive disease

PCR Polymerase chain reaction

PDE-4 Phosphodiesterase 4

PO Per orum – by mouth

PR Partial Response

PS Performance status

SAE Serious adverse event

Q.D. Every day

Q-PCR Quantitative Polymerase Chain Reaction

SPARC Secreted Protein Acidic and Rich in Cysteine

SD Stable disease

SWOG Southwest Oncology Group

TCR T-cell receptor

TGFβ Tumor growth factor beta

TNF Tumor necrosis factor

Page 14 of 86 Confidential

TPP Therapeutics Product Programme

TSH Thyroid-stimulating hormone

ULN Upper limit of normal

VEGF Vascular endothelial growth factor

WBC White blood cell

WCBP Women of child bearing potential

WHO World Health Organization

Page 15 of 86 Confidential

# 4 Background and Rationale

## 4.1. Multiple Myeloma

Multiple myeloma is a plasma cell neoplasm characterized by an infiltrate of monoclonal plasma cells in the bone marrow which results in the production of a monoclonal protein. Multiple myeloma accounts for approximately 10% of hematologic malignancies and about 1% of malignancies overall[1]. Approximately 19,000 patients will be diagnosed with multiple myeloma in 2007 in the United States and the median age at the time of diagnosis is 70 years (hence most patients with multiple myeloma are older than 65 years)[1]. Bone marrow involvement may result in cytopenias, painful skeletal lytic lesions and systemic symptoms (fevers, sweats, anorexia and weight loss); while the paraprotein may cause renal dysfunction, neuronal damage, amyloid deposition, and rarely hyperviscosity. The cornerstone of therapy of multiple myeloma has traditionally included the use of corticosteroids (prednisone or dexamethasone). However, these agents have substantial toxicities especially in the multiple myeloma patient population which tends to be particularly vulnerable to those side effects (namely fluid retention, non neutropenic infections and venous thromboembolic events). The past 5 years has witnessed the introduction of novel agents (lenalidomide, thalidomide and bortezomib) with considerable efficacy especially when combined with corticosteroids[2-4]. While these novel agents have considerably changed the outlook of multiple myeloma patients, the toxicity of therapy remains significant and attempts to reduce the toxicity of therapy by minimizing corticosteroid exposure remains a significant priority.

Page 16 of 86 Confidential

## 4.2. Lenalidomide

Version 6 4/15/2016

## 4.2.1 Preclinical evaluation of lenalidomide

Lenalidomide is a proprietary IMiD® compound of Celgene Corporation, which markedly stimulate T-cell proliferation, as well as IL-2 and IFN- $\alpha$  production, but do not inhibit phosphodiesterase 4 (PDE-4)[5]. Lenalidomide (Revlimid®) is 50 to 2000 times more potent than thalidomide in stimulating T-cell proliferation triggered via the T-cell receptor (TCR), and 50 to 100 times more potent than thalidomide in augmenting IL-2 and IFN- $\alpha$  production. In addition, Lenalidomide triggers dose-dependent decreased secretion of TNF- $\alpha$ , IL-1 $\beta$ , and IL-6; and triggers increased secretion of IL-10. The IC50 of Lenalidomide for inhibiting LPS induced TNF- $\alpha$  secretion by PBMC is ~100 nM (25.9 ng/mL), whereas thalidomide has an IC50 of ~194  $\mu$ M (50.2  $\mu$ g/mL)[6]. Lenalidomide decreases binding of MM cells to bone marrow stromal cells (BMSCs); inhibits the production in the BM milieu of cytokines (IL-6, VEGF, TNF- $\alpha$ ) mediating growth and survival of MM cells; blocks angiogenesis; and stimulates host anti-MM NK cell immunity[7, 8]. These preclinical studies suggest that Lenalidomide may overcome drug resistance, even to thalidomide, in MM cells.

## 4.2.2. Lenalidomide in relapsed refractory multiple myeloma

The immunomodulator lenalidomide has considerable activity in multiple myeloma. Early phase I study of single agent lenalidomide in relapsed refractory multiple myeloma have shown a response rate of approximately 30%[9, 10]. This single agent activity was confirmed in a subsequent phase II study evaluating two different doses of lenalidomide (15 mg once daily or 15 mg twice daily) for 21 of a 28 days cycle[9]. High dose dexamethasone (40 mg orally on days 1-4, 9-12, and 17-20) was added after 2 or 4 cycles in the event of disease progression or stable

Page 17 of 86 Confidential

disease respectively. Of 83 evaluable patients, 5 had a complete remission, 15 a partial remission, 14 had a minimal response, 39 had stable disease and the remainder had progressive disease. The rate of minimal response or better was 40%[9]. Dexamethasone was added to lenalidomide therapy in 30 non-responders, and resulted in a response in 10 patients (30% added response rate)[9]. The combination of lenalidomide and high dose dexamethasone was compared to high dose dexamethasone in two phase III trials in relapsed refractory multiple myeloma[11, 12]. This combination resulted in an overall response rate of approximately 60% and a complete response rate of 25% which was statistically superior to high dose dexamethasone[11, 12]. More importantly, the combination of lenalidomide and high dose dexamethasone resulted in an overall survival benefit compared to high dose dexamethasone[11, 12]. These results have led to the approval of lenalidomide by the Food and Drug Administration for the treatment of relapsed or refractory multiple myeloma.

#### **4.2.3 INDICATIONS AND USAGE:**

Revlimid® (lenalidomide) is indicated for the treatment of patients with transfusion-dependent anemia due to Low- or Intermediate-1-risk myelodysplastic syndromes associated with a deletion 5q cytogenetic abnormality with or without additional cytogenetic abnormalities. Revlimid® is also approved in combination with dexamethasone for the treatment of patients with multiple myeloma that have received at least one prior therapy.

## 4.2.4 Adverse Events

Most frequently reported adverse events reported during clinical studies with lenalidomide in oncologic and non-oncologic indications, regardless of presumed relationship to study medication include: anemia, neutropenia, thrombocytopenia and pancytopenia, abdominal pain,

Page 18 of 86 Confidential

nausea, vomiting and diarrhea, dehydration, rash, itching, infections, sepsis, pneumonia, UTI, Upper respiratory infection, atrial fibrillation, congestive heart failure, myocardial infarction, chest pain, weakness, hypotension, hypercalcemia, hyperglycemia, back pain, bone pain, generalized pain, dizziness, mental status changes, syncope, renal failure, dyspnea, pleural effusion, pulmonary embolism, deep vein thrombosis, CVA, convulsions, dizziness, spinal cord compression, syncope, disease progression, death not specified and fractures.

Complete and updated adverse events are available in the Investigational Drug Brochure and the IND Safety Letters.

## 4.2.5 Lenalidomide in newly diagnosed multiple myeloma

The phase II experience of lenalidomide and high dose dexamethasone in newly diagnosed multiple myeloma resulted in a response rate of 91% and generated interest in larger randomized studies evaluating this combination in this patient population[3]. The Eastern Cooperative Oncology Group randomized patients with newly diagnosed multiple myeloma to lenalidomide and low dose dexamethasone or lenalidomide and high dose dexamethasone[13]. The patients who received high dose dexamethasone in combination with lenalidomide had a superior response rate after 4 cycles of therapy (82% compared to 70% with low dose dexamethasone and lenalidomide, p<0.01), but had an inferior 1 year overall survival rate (87% versus 96%, p<0.001) and had a higher induction mortality (5% versus 0.5%, p=0.006)[13]. In addition, the patients who received high dose dexamethasone and lenalidomide had a higher rate of toxicity in the form of venous thromboembolic events, infectious complications, and neutropenia[13]. From these clinical observations, one can conclude that a better tolerated less intensive therapy will result in better survival (long term) outcomes in older adults with multiple myeloma.

Page 19 of 86 Confidential

# 4.2.6 Rationale for the evaluation of single agent lenalidomide in newly diagnosed mildly symptomatic multiple myeloma

While corticosteroids have been shown to result in apoptosis and decreased proliferation of multiple myeloma cells, they have also been noted to inhibit the stimulatory effects of lenalidomide on T cell and NK cell[14]. Hence, a lenalidomide based therapeutic approach excluding corticosteroids would take better advantage of the immunomodulatory effects of lenalidomide. In addition, clinical results corroborate such an approach: E4A03 study suggest that a lower dose of dexamethasone is associated with a superior survival outcome compared to higher dose of dexamethasone. These findings were more striking in older adults who are more vulnerable to the toxicities of dexamethasone (greater than 65 years of age)[13]. Accordingly, we propose to evaluate single agent lenalidomide in patients with newly diagnosed multiple myeloma who are only mildly symptomatic from their disease but who fulfill the requirement for active treatment initiation. This would be expected to result in better tolerance to therapy, less toxicity but more potential for eliciting the immunomodulatory effects of lenalidomide.

## 4.2.7 Measuring lenalidomide induced humoral immune response

Immunomodulation is one of the proposed mechanisms of action of lenalidomide and thalidomide in multiple myeloma. Because most of the clinical evaluations of lenalidomide in multiple myeloma have included concomitant corticosteroid use, firm evidence of immunomodulation and a lenalidomide induced tumor specific immune response has not been demonstrated *in vivo*. Noonan et al. have recently demonstrated enhanced humoral response to pneumococcal vaccination in multiple myeloma patients who received lenalidomide prior to vaccination as compared to patients receiving vaccination prior to lenalidomide therapy[15]. This data suggests an enhanced humoral immune response during lenalidomide therapy. Accordingly,

data suggests an enhanced humoral immune response during lenalidomide therapy. Accordingly, Version. 5.1 date 6/25/2014

Page 20 of 86 Confidential

we propose to evaluate the impact of lenalidomide monotherapy on the development of a humoral immune response directed to common tumor antigens.

## 4.2.7.1 Serametrix® serum profiling assay

The Serametrix serum profiling assay enables the multiplex detection of serum antibodies to key tumor antigens. The assay utilizes a proprietary protein microarray that contains protein antigens that are known to be immunogenic in cancer. The use of automated liquid handling equipment ensures high reproducibility, high throughput and low sample volumes. The assay has sufficient sensitivity and dynamic range to measure physiological levels of serum antibody and is therefore an effective tool in the measurement of humoral immune responses in cancer.

The Serametrix protein microarray contains approximately 100 tumor antigens. Each antigen is derived from sequence-verified full-length human clones. These are expressed in insect cells and the consequent eukaryotic glycosylation helps to ensure authentic epitopes are maintained. The proteins were selected from published scientific literature in consultation with leading academic tumor immunologists. The criteria for selection included demonstrable immunogenicity, association with cancer and suitability for use as biomarker.

## 4.2.8 Lenalidomide induced expression of tumor suppressor genes

A number of mechanisms of actions have been postulated to account for lenalidomide activity in multiple myeloma including direct tumor growth inhibition, upregulation of tumor suppressor genes and immunomodulation. Lenalidomide has been shown to induce the expression of various tumor suppressor genes (EGR1, EGR2, EGR3, p15, p21, p27 and SPARC) in multiple myeloma cells lines[14, 16, 17]. These studies have not been replicated in samples from patients and induction of these tumor suppressors could be an early predictor of response to lenalidomide. As

Page 21 of 86 Confidential

such, we propose to evaluate the expression of the above tumor suppressor genes after treatment of patients with single agent lenalidomide and correlate the induction of the tumor suppressor genes to clinical responses.

## 4.3. Corticosteroids in induction therapy for multiple myeloma.

The optimal dosage of corticosteroids in combination with lenalidomide in patients with newly diagnosed myeloma has not clearly been established. In older adults with multiple myeloma, several groups have attempted to investigate the optimal corticosteroid in induction therapy stemming from the lower tolerance to dexamethasone of older adults with multiple myeloma. One such investigation conducted by the national cancer institute of Canada compared induction therapy in older newly diagnosed multiple myeloma patients with melphalan and prednisone to therapy with melphalan and dexamethasone [18]. They noted a higher rate of grade 3 and 4 infections in the dexamethasone arm without a response or survival benefit to that agent[18]. Similar findings were reported by investigators of the Intergroupe Français du Myelome (IFM) who compared induction therapy with melphalan and prednisone compared to dexamethasone based therapy in older adults with multiple myeloma[19]. These results prompted us to evaluate prednisone as the corticosteroid partner of lenalidomide in patients who do not achieve a response after 2 cycles of single agent lenalidomide and yet have not evidence of disease progression. This combination was safely delivered as reported in two investigations where lenalidomide and alternate day prednisone were used as maintenance therapy in relapsed and newly diagnosed patients[20].

Page 22 of 86 Confidential

## 5. Study Endpoints

## **Primary:**

1- The 12-month progression free survival (PFS) of older adults with mildly symptomatic multiple myeloma treated on this response adapted approach (i.e. time from start of lenalidomide to failure of lenalidomide and low dose dexamethasone)

## **Secondary:**

- 1- The response rate of older adults with mildly symptomatic multiple myeloma to single agent lenalidomide, lenalidomide prednisone and lenalidomide low dose dexamethasone in patients with suboptimal responses to lenalidomide monotherapy
- 2- The toxicity profile of these lenalidomide based combinations
- 3- The progression free survival of patients treated with single agent lenalidomide
- 4- The 1 year overall survival (OS) of older adults with mildly symptomatic multiple myeloma treated on this response adapted approach

## **Exploratory**

- 1- Measure a lenalidomide induced tumor specific immune response and correlate the tumor specific immune response with corticosteroid use, response to therapy and duration of response
- 2- To evaluate the impact of lenalidomide mono-therapy on expression of tumor suppression genes and cell cycle regulators

[figure not shown]
Page 23 of 86 Confidential

## 6. Investigational Plan

## 6.1. Overall design

This is a phase 2 trial evaluating a lenalidomide based response adapted strategy in older adults with newly diagnosed multiple myeloma. Subjects will be started on single agent lenalidomide. In the event of disease progression, low dose dexamethasone will be added (see diagram below). In the event of stable disease after 2 cycles of therapy, the use of an alternate corticosteroid (prednisone) will be added to lenalidomide therapy (see diagram below). In the event of a minimal response after 2 cycles of single agent lenalidomide therapy, such therapy will be continued until disease progression (see diagram below).

Page 24 of 86 Confidential

Subject replacement and evaluable patients

Subjects who discontinue study drug, other then for progression, prior to completing one cycle of therapy will be replaced.

# **6.2.** Discussion of design

Older adults or subjects not willing or eligible for post induction high dose therapy and stem cell transplantation will be offered participation into this study. This is in line with findings from the ECOG E4A03 study which noted a decreased survival among patients receiving higher dose dexamethasone compared to low dose dexamethasone specifically in the subgroup of patients older than 65 years of age[13]. In addition, patients enrolled on this response adapted clinical

Page 25 of 86 Confidential

trial would be either not willing or ineligible to undergo *immediate* (post 4 cycles of induction) high dose therapy and stem cell transplantation. The rationale underlying this exclusion criterion related to the fact that patients wishing to undergo *immediate* (post induction) high dose therapy usually are treated with more aggressive front line regimens.

Mildly symptomatic patients will be selected for participation in this study. The rationale for the selection of this population lies in the fact that patients with aggressive disease at presentation (patients with significant symptoms) are probably best treated with combination therapy in order to achieve a higher likelihood of response (as evidenced by E4A03 where patients receiving higher dose dexamethasone in combination with lenalidomide had a higher response rate than patients receiving a lower dose of dexamethasone in combination with lenalidomide)[13]. Empirically, defining this patient population objectively can be difficult but we propose the following definition of mildly symptomatic disease: good performance status (ECOG 0-1), absence of severe cytopenias or renal failure, as well as low risk as defined by β2-microglobulin level and lack of adverse cytogenetic features[21].

In addition, this study will evaluate the role of an alternative corticosteroid in combination with lenalidomide. Prednisone is known to be a better tolerated corticosteroid than dexamethasone without a compromise in the efficacy. This was seen in a recent report of a clinical trial by the national cancer institute of Canada study comparing melphalan prednisone to melphalan dexamethasone (grade 3 and 4 infections; 9 versus 15%, p=0.03)[18]. In addition, the intergroupe francais du myelome (IFM) had noted similar finding in older adults with newly diagnosed myeloma randomized to melphalan prednisone or dexamethasone based induction[19]. Both trials did not note a superiority of dexamethasone based induction to the prednisone based induction.

Page 26 of 86 Confidential

The primary endpoint of this study will be the progression free survival of patients treated with this response adapted approach. This is defined as the time from enrollment to failure of lenalidomide and low dose dexamethasone. Outcomes of this cohort of patients treated with this response adapted approach would be compared to patients treated with lenalidomide and low dose dexamethasone. If this response adapted approach results in similar or improved outcomes compared to therapy with lenalidomide and low dose dexamethasone, this approach would be favored since it likely result in less toxicity by using an overall lower dosage of corticosteroid.

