#### STUDY DESIGN:

This is a multi-center, single-arm, phase 2, open-label study of lenalidomide [Revlimid® (R)] based therapy in older adults with standard risk multiple myeloma. After enrollment patients will receive single agent lenalidomide. Responders (minimal response or better) after 2 cycles will continue present therapy until disease progression or intolerable toxicity. Patients with stable disease after 2 cycles will receive prednisone (100 mg orally on days 1 to 5 of each cycles) in addition to lenalidomide. Patients with evidence of disease progression after 2 cycles of single agent lenalidomide will receive low dose dexamethasone (40 mg weekly) in addition to lenalidomide. Patients not receiving low dose dexamethasone and with disease progression at any time during the study will be eligible to receive low dose dexamethasone in combination with lenalidomide. Patients on lenalidomide and low dose dexamethasone who experience disease progression at any time during the study will be taken off study and treated with alternative therapies..

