#### 7.1.1. Inclusion criteria

Subjects must meet all of the following inclusion criteria to be eligible for enrollment into the study:

- 1. Understand and voluntarily sign an informed consent form.
- 2. Age  $\geq$ 65 years or not eligible for high dose therapy and autologous stem cell transplant.
- 3. Able to adhere to the study visit schedule and other protocol requirements.

Page 27 of 86 Confidential

4. Diagnosed with multiple myeloma and be considered to have active disease. Patients must not have received an active chemotherapy regimen or Dexamethasone. Patients may have received palliative radiotherapy at least 2 weeks prior to the study start.

- Measurable myeloma paraprotein levels in serum (≥ 0.5 g/dL), urine (≥ 0.2 g excreted in a 24-hour urine collection sample) or by serum free light chains (involved free light chain greater than 100mg/L)
- 6. Eastern Cooperative Group (ECOG) Performance Status of 0 or 1.
- Serum bilirubin levels ≤1.5 times the upper limit of the normal range for the laboratory (ULN).
- 8. Serum AST or serum ALT] levels  $\leq 2 \times \text{ULN}$
- 9. Must have adequate bone marrow function:
  - a. Absolute neutrophil count  $> 1,000 \text{ cells/mm}^3 (1.0 \text{ x } 10^9/\text{L}).$
  - b. Platelets  $\geq 100,000 \text{ /mm}^3$ .
- 10. Hemoglobin > 8 g/dL
- 11. Must have adequate renal function: Renal function assessed by calculated creatinine clearance as follows (see Appendix VI: Cockcroft-Gault estimation of CrCl):
  - a. Calculated creatinine clearance ≥ 30ml/min by Cockcroft-Gault formula. See section below, "Prescribing Information", regarding lenalidomide dose adjustment for calculated creatinine clearance ≥ 30ml/min and < 60ml/min.
- 12. Low risk myeloma is defined as the absence of the following adverse features[21]
  - i. t(4;14) by FISH or metaphase cytogenetics
  - ii. t(14,16) or t(14;20) by FISH or metaphase cytogenetics
  - iii. Deletion 17q13 by FISH
  - iv. Deletion 13 by metaphase analysis
  - v. Aneuploidy by metaphase analysis

Page 28 of 86 Confidential

- vi. B2 microglobulin > 5.5
- 13. Able to tolerate one of the following thromboprophylactic strategies: aspirin, low molecular weight heparin or warfarin (coumadin).
- 14. All study participants must be registered into the mandatory RevAssist® program, and be willing and able to comply with the requirements of RevAssist®.

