## 12.1. Sample size:

The primary endpoint is 12-month PFS for the overall response adaptive approach. Based on the E4A03 and SWOG 2032 studies, the 12-month PFS is approximately 70% for patients treated with lenalidomide low dose dexamethasone. The sample size determination is primarily based on the consideration of providing an estimate of the 12-month PFS with reasonable precision. We estimate the 12-month PFS in the response adapted approach is 85%. With a sample size of 60 evaluable patients (30 from Moffitt and 30 from sites in South Korea), its 95% confidence interval is 73.4-92.9%.

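### Section 6.2 would favour the response-adapted approach if it does as well as lenalidomide plus low-dose dexamethasone, but the only PFS figure for that regimen is not shown to come from comparably selected patients

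*Combined protocol and SAP*

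**What the plan says.** The synopsis describes the design: "This is a multi-center, single-arm, phase 2, open-label study of lenalidomide". There is no concurrent control.

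Section 6.2 nevertheless plans a comparison: "Outcomes of this cohort of patients treated with this response adapted approach would be compared to patients treated with lenalidomide and low dose dexamethasone". It then gives the conclusion to be drawn. If the strategy "results in similar or improved outcomes compared to therapy with lenalidomide and low dose dexamethasone, this approach would be favored", the reason being lower expected steroid exposure and toxicity. It gives no margin for similarity, and it does not say which Ld patients are meant.

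Section 12.1 supplies the only Ld PFS figure, attributed to E4A03 and a SWOG study: "the 12-month PFS is approximately 70% for patients treated with lenalidomide low dose dexamethasone". It projects 85% for the response-adapted approach and sizes the trial on precision, with 60 patients and a 95% interval of 73.4-92.9%. Section 4.2.5 gives other E4A03 outcomes for Ld (70% response after 4 cycles, 96% one-year survival). It says of that trial's population only that the group "randomized patients with newly diagnosed multiple myeloma to lenalidomide and low dose dexamethasone or lenalidomide and high dose dexamethasone".

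Entry to this trial is narrower. Criterion 12 in Section 7.1.1 reads "Low risk myeloma is defined as the absence of the following adverse features" and lists t(4;14), t(14;16) or t(14;20), a chromosome 17 deletion, deletion 13, aneuploidy and beta-2 microglobulin above 5.5. Criterion 6 requires ECOG 0 or 1. Section 6.2 confines the trial to mildly symptomatic patients on the ground that "patients with aggressive disease at presentation (patients with significant symptoms) are probably best treated with combination therapy".

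**The concern.** A preference between two treatments is to be read from one treated group and an outside rate. That works only if the outside patients would have had about the same outcome as the enrolled patients on the same treatment. The protocol itself calls the excluded features adverse, yet nothing shows that the 70% comes from patients without them.

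If standard-risk, mildly symptomatic patients given Ld from the start would exceed 70% at 12 months, a result at or above 70% cannot separate an effective steroid-sparing strategy from good-prognosis selection. The conclusion in 6.2 could then favour the strategy even where it does worse than Ld in the patients enrolled.

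Nothing in Section 12 deals with this. The logistic and Cox models in 12.2.2 relate outcomes to covariates within the trial. Section 12.2.4 tests and adjusts for Moffitt versus South Korea only, and its remark that the groups should be comparable concerns those two groups.

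**Working it through.** **The plan's own figure.** 85% of 60 is 51. The exact (Clopper-Pearson) 95% interval for 51/60 is 73.4-92.9%, as stated in 12.1. It lies wholly above 70%.

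**What 70% overall could mean for patients like these.** Let f be the share of historical patients whom this trial would exclude, and p their 12-month PFS. Then

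0.70 = (1 - f) × r + f × p, so r = (0.70 - f × p) / (1 - f),

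where r is the Ld rate in the remainder. The documents give neither f nor p; the values below are assumptions.

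| f | p = 40% | p = 50% | p = 60% |
|---|---|---|---|
| 20% | 77.5% | 75.0% | 72.5% |
| 30% | 82.9% | 78.6% | 74.3% |
| 40% | 90.0% | 83.3% | 76.7% |

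For example, f = 30% and p = 50% give (0.70 - 0.15)/0.70 = 78.6%. The range is 72.5% to 90%.

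**Set against the projected interval.** 73.4-92.9% contains every cell except the lowest, (0.70 - 0.12)/0.80 = 72.5%. A nearby case, f = 25% and p = 60%, gives (0.70 - 0.15)/0.75 = 73.3%, which is also just outside. Elsewhere in the table the projected result would not exclude equality with Ld in like patients.

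**Selection alone reaching 85%.** This needs f = 0.15/(0.85 - p): 33% at p = 40%, 43% at p = 50% and 60% at p = 60%. Only the first lies inside the assumed range.

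**How often the rule would be met, n = 60.** Section 6.2 sets no threshold. I read it in two ways: observed rate at least 70% (42/60), or exact lower 95% limit above 70% (50/60). Exact binomial probabilities are:

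| True rate in this trial | Observed ≥ 70% | Lower limit > 70% |
|---|---|---|
| 70% | 56% | 1.4% |
| 75% | 85% | 9% |
| 80% | 98% | 32% |
| 85% | 99.9% | 72% |

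- No benefit over Ld, but selection puts both at 80% (for example f = 25%, p = 40%: (0.70 - 0.10)/0.75 = 80%). The observed rate is at least 70% with probability 98%, and the lower limit clears 70% with probability 32%.
- Ld would give 80% in these patients and the strategy only 70%. The strategy is 10 points worse and still shows at least 70% with probability 56%.

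**Whether the endpoints match.** The synopsis and Section 5 run PFS from the start of lenalidomide, and 6.2 from enrolment, in each case to failure of lenalidomide plus low-dose dexamethasone. Section 12.2.1 runs from the start of lenalidomide to first progression or death. Progression before dexamethasone is added counts as an event in 12.2.1 but not under the other wording. The documents do not say which definition lies behind the 70%.

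**The case against.** The formal plan is estimation. The primary objective is to estimate efficacy, 12.1 sizes for precision, and 12.2.1 reports a rate with its interval. No test or threshold uses 70%, and 6.2 names no figure, so linking 6.2 to 70% is an inference. That is fair. But 6.2 does state what will be concluded, and 12.1 offers the 70% for the very comparator that 6.2 names.

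The risk mix of the historical studies is not given, so both f and p are assumed. This stands and limits the claim to what selection can do. A reader might infer that the 70% is an unselected-population rate. The documents do not establish that: Section 4.2.5 is silent on risk criteria for E4A03, and nothing describes the SWOG study's patients.

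Age may offset the selection. Entry requires age 65 or over, or ineligibility for high-dose therapy and transplant. Section 6.2 refers to an over-65 subgroup of E4A03, so that trial also had younger patients. This stands too; the table above models favourable selection only.

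Accrual at Moffitt is complete. The Amendment 6 rationale says, however, that a manuscript is still to be published, so the interpretive wording still matters.

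**Conclusion.** The point holds as a limit on what may be concluded. The 12-month PFS estimate and its interval are unaffected. The comparative conclusion in 6.2 is not supported by the planned analysis, because a result similar to or better than about 70% can arise from patient selection, and nothing planned would detect or correct that.

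On the assumed inputs, the Ld rate in like patients would be 72.5-90%. The projected interval includes most of that range but not the lowest values (72.5-73.3%). The apparent gain over 70% therefore may not hold against a risk-matched benchmark. A reader might go further and infer that the gain does vanish, or that the comparison is biased in the strategy's favour. Neither follows: the first fails at the low end of the assumed range, and the net direction is unknown because the historical mix is not given and age may act the other way. Nor is 70% PFS the only Ld outcome in the documents. It is the only Ld PFS figure; Section 4.2.5 gives response and one-year survival, also without stating a risk restriction.

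**What to change.** 1. Reconcile the PFS definition between the synopsis, Section 5 and Section 6.2 on one side and Section 12.2.1 on the other. No comparison with an outside rate is interpretable until this is done.
2. In 6.2, replace the sentence on which approach would be favoured. State that 12-month PFS is reported as an estimate with its 95% interval and that any comparison with Ld is descriptive. Add that similarity or superiority to Ld will not be concluded unless the Ld figure comes from patients meeting this trial's risk, performance-status and age criteria and uses the same PFS definition.
3. In 12.1, add that the 70% figure is not shown to be risk-matched to this cohort. Do not label it as unselected, since the documents do not show that either.

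The cost is a weaker comparative claim. These are wording changes, with no added patients or procedures. A matched comparison, if wanted, would need subgroup or patient-level data from the historical studies; the fix does not require it.
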